7.3 Randomization

Approximately 65 subjects, of which up to 15 subjects have F/RF genotypes, will be stratified by genotype and randomized 4:1 to study drug treatment.

An interactive web or voice response system (IXRS) will be used to assign subjects to treatment. Detailed instructions for randomization will be provided separately.

7.4 Blinding and Unblinding

Refer to Section 10.8 of the CSP for details.

8 ANALYSIS SETS

The following analysis sets are defined: All Subjects Set, Full Analysis Set, and Safety Set.

8.1 All Subjects Set

The All Subjects Set will be defined as all subjects who were randomized or received at least 1 dose of study drug. This analysis set will be used for all individual subject data listings and the disposition summary table, unless specified otherwise.

8.2 Full Analysis Set

The Full Analysis Set (FAS) will be defined as all subjects who were randomized and received at least 1 dose of study drug and had an eligible genotype. The FAS will be used for all efficacy analyses and subjects will be analyzed according to the treatment arm they are randomized to.

8.3 Safety Set

The Safety Set will be defined as all subjects who received at least 1 dose of study drug. The Safety Set will be used for all safety analyses, unless otherwise specified. The subjects will be analyzed according to the treatment they received.

9 STATISTICAL ANALYSIS

9.1 General Considerations

The Schedule of Assessments is provided in the clinical study protocol (CSP) Table 3-1. Individual subject data for subjects in the All Subjects Set will be presented in individual subject data listings. The precision standards are provided in [Appendix B](#).

Continuous variables will be summarized using the following descriptive summary statistics: the number of subjects (n), mean, standard deviation (SD), median, minimum value (min), and maximum value (max).

Categorical variables will be summarized using counts and percentages.

Baseline value, unless specified otherwise, will be defined as the most recent non-missing measurement (scheduled or unscheduled) collected before the first dose of study drug. For ECGs, the baseline value will be defined as the average of the non-missing pretreatment measurements (triplicate) on Day 1.

Absolute change from baseline will be calculated as Post-baseline value – Baseline value.

Relative change from baseline will be calculated and expressed in percentage as 100% × (Post-baseline value – Baseline value) / Baseline value.

Treatment-emergent (TE) Period will include the time from the first dose to 28 days after the last dose of the study drug or to the completion of study participation date, whichever occurs first. Completion of study participation is defined as one of the following:

- For subjects who complete the study and enroll in the extension study within 28 days of the Week 8 Visit: the last participation date
- For subjects who complete the study and do not enroll in the extension study within 28 days of the Week 8 Visit: the Safety Follow-up Visit
- For subjects who prematurely discontinue study drug treatment but do not withdraw consent: the latest of ETT Visit, or Safety Follow-up Visit (if required)
- For subjects who withdraw consent: date of withdrawal of consent

The TE period will be used for safety analyses unless specified otherwise.

Unscheduled visits: Unscheduled visit measurements will be included in analysis as follows:

- In scheduled visit windows per specified visit windowing rules.
- In the derivation of baseline/last on-treatment measurements.
- In the derivation of maximum/minimum on-treatment values and maximum/minimum change from baseline values for safety analyses.
- In individual subject data listings as appropriate.

Visit windowing rules: The analysis visit windows for protocol-defined visits are provided in [Appendix A](#).

Incomplete/missing data will not be imputed, unless specified otherwise.

Outliers: No formal statistical analyses will be performed to detect or remedy the presence of statistical outliers, unless specified otherwise.

Multiplicity: No multiplicity adjustment will be performed for hypothesis testing.

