**Table 3-1 Study VX16-661-115: Screening, Treatment Period, Early Termination of Treatment, and Safety Follow-up**

Event/Assessment a	Treatment Period					Early Termination of Treatment (ETT) Visit b	Safety Follow-up Visit (4 Weeks [± 7 Days] After Last Dose of Study Drug) c
	Screening Period Day -28 to Day -1	Day 1	Week 2 (± 3 Days)	Week 4 (± 5 Days)	Week 8 (± 5 Days) d		
Urinalysis o	X	X			X	X	X
Lipid panel o		X p			X	X	X
Vitamin levels o		X p			X	X	X
Serum chemistry o	X	X p	X	X	X	X	X
Hematology o	X	X p	X		X	X	X
Coagulation studies o	X				X	X	X
Multiple-breath washout (MBW) s	X	X	X	X	X		
Spirometry t	X	X	X	X	X	X	X
Meal or snack at clinic		X	X	X	optional		
Study drug count			X	X	X	X	

o See Section 11.5.2 for details.

p Blood samples to be collected predose on Day 1. At all other scheduled visits, these samples will be collected at any time during the visit.

s The MBW assessment will be performed in multiple replicates and before study drug dosing (see Section 11.4.1 and the Study Reference Manual). MBW should be performed pre-bronchodilator and will be performed before the spirometry assessment.

t At the Screening Visit, spirometry may be performed pre- or post-bronchodilator. At all visits during the Treatment Period, spirometry must be performed for all subjects before dosing and should be performed pre-bronchodilator. On Day 1 and Week 2, additional spirometry will be performed at 2 (± 30 minutes) and 4 hours (± 30 minutes) postdose. If more than 1 spirometry assessment is required at a visit, bronchodilators should be withheld until the last scheduled spirometry assessment is completed. If study drug is not administered on the day of the visit (i.e., study drug interruption or permanent discontinuation of study drug) the assessment will only be collected once.

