    - o Persistent chest radiograph abnormalities consistent with CF pulmonary disease (e.g., bronchiectasis, atelectasis, infiltrates, hyperinflation)
    - o Nasal polyps, chronic sinusitis as manifest by radiographic or computed tomographic abnormalities of the paranasal sinuses
    - o Evidence of gastrointestinal disease consistent with the diagnosis of CF
    - o Significant delays in growth and/or weight gain consistent with the diagnosis of CF
9. Subjects with ppFEV1 of  $\geq 70$  percentage points adjusted for age, sex, height, and ethnicity using the Global Lung Function Initiative (GLI) equation at the Screening Visit (Section 11.4.2).
  10. Subjects with a screening LCI2.5 result  $\geq 7.5$ .
  11. Subjects with stable CF disease as deemed by the investigator at the Screening Visit.
  12. Subjects who are willing to remain on their stable CF medication regimen through Week 8 or, if applicable, through the Safety Follow-up Visit.
  13. Subjects who are able to swallow tablets.
  14. Female subjects of childbearing potential must have a negative serum pregnancy test at the Screening Visit and a negative urine pregnancy test at the Day 1 Visit before receiving the first dose of study drug.
  15. Subjects of childbearing potential who are sexually active must meet the contraception requirements outlined in Section 11.5.8.1.
  16. As deemed by the investigator, the subject's legally appointed and authorized representative (e.g., parent or legal guardian) must be able to understand protocol requirements, restrictions, and instructions. The subject's legally appointed and authorized representative should be able to ensure that the subject will comply with and is likely to complete the study as planned.

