### 9.1.1 Screening

Screening Visit assessments are listed in [Table 3-1](#).

The Screening Period will occur within 28 days before the first dose of study drug to confirm that subjects meet the selection criteria for the study. To participate in the study, the subject's parent or legal guardian must sign and date a study-specific ICF and the subject must sign an assent form (if applicable) before any study-specific procedures can be performed. The ICF (and assent form, if applicable) will comply with all applicable regulations governing the protection of human subjects and will be approved by Vertex and the site's IRB.

To prepare for study participation, subjects will be instructed on the study restrictions ([Section 9.4](#)) and use of concomitant medications ([Section 9.5](#)). During the Screening Period, subjects who are being treated with Orkambi or Kalydeco will undergo a 28-day washout before the Day 1 Visit ([Table 9-1](#)).

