### 9.1.1.1 Repetition of Screening Period Assessments

Repetition of any individual Screening Visit assessment(s) that does not meet eligibility criteria is not permitted, with the following exceptions:

- If there is clear evidence of a laboratory error (e.g., hemolyzed sample) or equipment malfunction, collection of a repeat sample for the appropriate laboratory test may be permitted after discussion with the Vertex medical monitor or authorized designee.
- If a convincing alternative etiology is identified for elevated transaminases, exclusionary liver function test (LFT) levels may be retested within 14 days of the original Screening Visit date.
- If screening spirometry measurements fail to meet acceptability and repeatability criteria as specified by the American Thoracic Society (ATS)/European Respiratory Society (ERS) guidelines, repeat spirometry evaluation may be performed once.
- If the subject had difficulty completing the multiple-breath washout (MBW) assessment.
- Patients taking physician-prescribed Orkambi or Kalydeco at the Screening Visit can repeat the screening MBW and sweat chloride assessments as needed after approximately 28 days of Orkambi washout.

If repeat values of the individual assessment(s) are within the eligibility criteria and completed within the Screening Period window, then the subject is eligible for the study.

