#### **11.4.3 Sweat Chloride**

The sweat chloride test is a standard diagnostic tool for CF, serving as a biomarker of CFTR activity. Collection of sweat samples will be performed at visits specified in [Table 3-1](#) using an approved collection device. Sweat samples will be sent to a central laboratory for testing and interpretation of results. Individual sweat chloride test results will not be disclosed to the study sites. Specific instructions for collection, handling, processing, and shipping of sweat chloride samples will be provided in a separate Laboratory Manual.

The sweat chloride test must be conducted before dosing with study drug at visits during the Treatment Period. At each time point, 2 samples will be collected, 1 sample from each arm (left and right). During the Treatment Period, sweat collection will be done approximately at the same time as predose blood collections.

Collection of sweat chloride will not overlap with any other study assessments.

Subjects and their parent/caregiver should not be informed of their study-related sweat chloride results during the Treatment Period.

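### The LCI2.5 and sweat chloride baseline rule has no washout condition, so when a Day 1 value is missing a Screening value taken on Orkambi or Kalydeco can become baseline

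*SAP*

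**What the plan says.** SAP 9.1 and Protocol 12.3.1 give one rule for every variable except ECG: baseline "will be defined as the most recent non-missing measurement (scheduled or unscheduled) collected before the first dose of study drug". ECG has its own definition, tied to Day 1. The visible text has none for LCI2.5 or sweat chloride. In SAP Appendix A the Day 1 window for both takes in any record up to Day 1 pre-dose, with no lower limit.

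Protocol 9.1.1 places the modulator washout after the Screening Visit: "During the Screening Period, subjects who are being treated with Orkambi or Kalydeco will undergo a 28-day washout before the Day 1 Visit". Protocol 9.1.1.1 recognises that tests at Screening may be on drug. Children taking a modulator then "can repeat the screening MBW and sweat chloride assessments as needed after approximately 28 days of Orkambi washout". That repeat is optional and serves eligibility. Inclusion criterion 10 requires a Screening LCI2.5 of at least 7.5.

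Both tests are also scheduled on Day 1. For MBW, Table 3-1 states: "The MBW assessment will be performed in multiple replicates and before study drug dosing". For sweat chloride, Protocol 11.4.3 states: "The sweat chloride test must be conducted before dosing with study drug at visits during the Treatment Period".

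Under SAP 9.3.1 the study succeeds if the upper 95% limit of the TEZ/IVA group's mean change lies below -0.10. The placebo group is only summarised.

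**The concern.** The protocol allows for on-drug Screening tests when it judges eligibility, but the analysis rule does not carry this over to baseline. A child already at or above 7.5 on drug has no need to repeat the test. If that child's Day 1 MBW then fails or is not done, the on-drug Screening result is the most recent non-missing value and becomes baseline. The change score then sets TEZ/IVA against another modulator instead of against the untreated state. The same can happen with sweat chloride.

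A second, milder problem arises when the fallback value is the LCI that qualified the child. Values selected for being at or above a limit tend to be lower on retest even without any drug effect.

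The primary result is one group's change against a fixed number. No concurrent comparison cancels a baseline error, and the baseline covariate in a one-group model does not remove it. The two errors have opposite signs, but nothing makes them offset.

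**Working it through.** **1. The plan's own figure.** Inputs from SAP 7.2: true mean change -0.9, reference -0.10, SD 1.41, two-sided alpha 0.05, about 40 children, 10% dropout. Evaluable: 40 x 0.9 = 36. SE = 1.41/√36 = 0.235. Power (normal) = Φ(0.8/0.235 - 1.96) = 92.6%; with the noncentral t it is 91.1%. The stated power of at least 90% reproduces, and this point does not challenge it.

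**2. When the fallback applies.** Washout must be complete before the Day 1 Visit, and both tests are scheduled that day before dosing. A child with a usable Day 1 value therefore has an off-modulator Day 1 baseline. The fallback needs a missing Day 1 value. The documents give no rate for this, so the number affected, k, is an assumption. The denominator is the planned TEZ/IVA group in Protocol Table 12-1: 40 F/F + 12 F/RF = 52.

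**3. On-modulator baseline.** Assume the earlier modulator lowered LCI2.5 by 0.9, the effect SAP 7.2 assumes for TEZ/IVA. Each affected change score is then too high by 0.9. The shift in the mean is k/52 x 0.9.

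| k | Shift | Power, 36 evaluable (t) |
|---|---|---|
| 0 | 0 | 91.1% |
| 1 | +0.017 | 89.9% |
| 2 | +0.035 | 88.6% |
| 5 | +0.087 | 83.9% |

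**4. Qualifying value as baseline.** The documents give no LCI mean, between-child SD or test error, so all three are assumed. Let μ be the true mean, s_t the between-child SD and s_e the test-error SD, with s_x² = s_t² + s_e² and a = (7.5 - μ)/s_x. The expected error of a value selected at 7.5 or above is (s_e²/s_x) x φ(a)/(1 - Φ(a)).

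| μ | s_t | Error, s_e = 0.5 | Error, s_e = 1.0 |
|---|---|---|---|
| 9 | 1.5 | 0.05 | 0.20 |
| 8.5 | 1.0 | 0.07 | 0.29 |
| 7.6 | 0.8 | 0.19 | 0.58 |

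For example, with μ = 8.5, s_t = 1.0 and s_e = 1.0: s_x = 1.414, a = -0.707, and (1/1.414) x 0.3107/0.7602 = 0.29. The upper s_e is 1.41/√2 = 1.0, which treats the whole SD of change as noise. MBW is done in replicates, so this is likely too high. The last row puts the population almost at the cut-off and is an extreme case.

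For 2 of 52 children, the shift in the mean is 2/52 x 0.29 = 0.011 or 2/52 x 0.58 = 0.022, in favour of TEZ/IVA. The one-sided false-success rate at a true mean of -0.10 (36 evaluable, t) rises from 2.5% to 2.8% or 3.1%.

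**5. How many children would make it large.** To use up 0.10 in the group mean, the qualifying-value route needs 0.10 x 52/0.29 = 17.9, so about 18 children, or 0.10 x 52/0.58 = 9.0, so about 9 at the extreme.

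**The case against.** The strongest reply is that the schedule already prevents nearly all of this. Day 1 MBW and sweat chloride are planned, pre-dose and after washout, and a most-recent-value rule picks them. Note 4 to Appendix A points the same way: among several efficacy records in a window, the one at the scheduled visit is used, otherwise the one closest to the target day. This stands, and it is why the effect is small. It does not help the child whose Day 1 value is missing.

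An on-modulator LCI baseline also works against TEZ/IVA and cannot create a false success. That is correct, but it still gives that child a wrong change score. For sweat chloride the route is narrower, because Table 3-1 makes the Screening test optional when a recorded value establishes eligibility.

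The rule applies unless specified otherwise, and parts of both documents are redacted, so a variable-specific rule may exist out of sight. That cannot be excluded.

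Two stronger readings are tempting and are not supported:

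- A reader might infer that the post-washout repeat MBW can double as the Day 1 test, so that one high reading both qualifies the child and serves as baseline. Table 3-1 gives Screening (Day -28 to Day -1) and Day 1 separate MBW tests. Protocol 9.1.1.1 requires repeats to be completed within the Screening window, and 9.1.1.3 allows a 2-week extension for repeats.
- A reader might set the per-child errors of 0.05 to 0.58 beside the 0.10 allowance. That allowance applies to the group mean, so the errors must first be scaled by the share of children affected.

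**Conclusion.** The gap is real but narrow. As written, the rule lets an on-modulator Screening value become the LCI2.5 or sweat chloride baseline, and it also lets the qualifying LCI become baseline, but only for children whose Day 1 value is missing. With 2 of 52 affected, the primary mean moves by about +0.035 (against TEZ/IVA, if the modulator effect is 0.9) or by about -0.01 to -0.02 (in its favour, at 0.29 to 0.58 per child). All these inputs are assumed. The documents do not show that the trial's conclusion is at risk or that its power statement is wrong. No size can be given for sweat chloride, because the documents give no modulator effect on it. The correction is worth making because it costs almost nothing and must be fixed before unblinding; choosing afterwards which baselines count would be data-driven.

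**What to change.** In SAP 9.1, add for LCI2.5 and sweat chloride:

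- A value obtained before the protocol-required modulator washout is complete cannot serve as baseline.
- Baseline is the Day 1 pre-dose value. If that is missing, it is the most recent pre-dose value obtained off modulator after any required washout. A Screening value remains usable in a child who was not taking a modulator.
- The number of children whose baseline is not from Day 1 will be reported.
- A sensitivity analysis of the primary endpoint will exclude children whose baseline LCI2.5 is the qualifying Screening value.

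Barring every Screening value outright would discard usable data, so the qualifying-value issue belongs in the sensitivity analysis. Protocol 9.1.1.1 needs no change.

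Cost: a short addition to the SAP, with no new visit or test. The rare child with no valid off-modulator baseline stays in the FAS but gives no change score. Losing one of 52 widens the standard error by √(52/51) - 1, about 1%.

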### 9.1.4 Early Termination of Treatment

If the subject prematurely discontinues study treatment, an Early Termination of Treatment (ETT) Visit should be scheduled as soon as possible after the subject decides to terminate study treatment. Subjects who prematurely discontinue treatment will also be required to complete the Safety Follow-up Visit, approximately 4 weeks  $\pm 7$  days after their last dose of study drug. If the ETT Visit occurs 3 weeks or later after the last dose of study drug, then the Safety Follow-up Visit will replace the ETT Visit and a separate ETT Visit is not required. Subjects who prematurely discontinue treatment will continue to complete all the other scheduled study visits for assessments of efficacy as detailed in the Schedules of Assessments ([Table 3-1](#)).

During the course of study conduct, if local health authorities decline to approve, or if clinical benefit is not demonstrated for the use of TEZ/IVA for the treatment of CF in a corresponding adult population, pediatric subjects with the relevant *CFTR* genotypes may be discontinued after communication to investigators and IRBs/IECs of the risks/benefits related to the safety and efficacy observed for the subset of subjects. If subjects are discontinued from the study, an ETT Visit should occur as soon as possible after the last dose of study drug and a Safety Follow-up Visit should occur approximately 4 weeks  $\pm 7$  days after the last dose of study drug. Subjects who are discontinued due to having an ineligible genotype or due to lack of health authority approval ([Section 9.8](#)) will complete the ETT Visit and are not required to return for additional efficacy assessments, because they will be discontinued from the study.

If the subject withdraws consent for the study no further evaluations should be performed, and no additional data should be collected. Vertex may retain and continue to use any data collected before such withdrawal of consent.

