#### 12.3.1 General Considerations

The precision standards for reporting safety and efficacy variables are provided in an internal Biometrics document that specifies the programming rules including the precision for derived variables.

All individual subject data for subjects who were randomized or received at least 1 dose of study drug will be presented in individual subject data listings.

**Continuous variables** will be summarized using the following descriptive summary statistics: the number of subjects (n), mean, SD, SE, median, minimum value (min), and maximum value (max).

**Categorical variables** will be summarized using counts and percentages.

**Baseline value**, unless specified otherwise, will be defined as the most recent non-missing measurement (scheduled or unscheduled) collected before the first dose of study drug. For ECGs, the baseline value will be defined as the average of the non-missing pretreatment measurements (triplicate) on Day 1.

**Change (absolute change) from baseline** will be calculated as Post-baseline value – Baseline value.

**Relative change from baseline** will be calculated and expressed in percentage as 100% × (Post-baseline value – Baseline value)/Baseline value.

**Treatment-emergent (TE) Period** will include the time from the first dose to the earliest of the following: the Safety Follow-up Visit, or 28 days after the last dose of the study drug for subjects who do not have a Safety Follow-up Visit. The TE period will be used for safety analyses unless specified otherwise.

**Unscheduled visits:** Unscheduled visit measurements will be included in analysis as follows:

- In scheduled visit windows per specified visit windowing rules.
- In the derivation of baseline/last on-treatment measurements.
- In the derivation of maximum/minimum on-treatment values and maximum/minimum change from baseline values for safety analyses.
- In individual subject data listings as appropriate.

**Visit windowing rules:** The analysis visit windows for protocol-defined visits will be provided in the SAP.

**Incomplete/missing data** will not be imputed, unless specified otherwise.

**Outliers:** No formal statistical analyses will be performed to detect or remedy the presence of statistical outliers, unless specified otherwise.

**Multiplicity:** No multiplicity adjustment will be performed for hypothesis testing.

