### 13.1.1.3 Documentation of Adverse Events

All AEs will be collected from the time ICF is signed until the following time points:

- For subjects who do not enroll: until time of screen failure (e.g., screen failure, withdrawal of consent)
- For enrolled subjects who have a Safety Follow-up Visit: through the Safety Follow-up Visit
- For enrolled subjects who do not have a Safety Follow-up Visit, the earliest of
  - o 28 days after the last dose of study drug, or
  - o the ETT Visit, if that visit is 3 weeks or later following the last dose of study drug (see [Section 9.1.4](#))

All subjects will be queried, using nonleading questions, about the occurrence of AEs at each study visit. When possible, a constellation of signs and/or symptoms will be identified as 1 overall event or diagnosis. All AEs for enrolled subjects will be recorded in the CRF and source document. AEs for subjects who are screened but not subsequently enrolled in the study will be recorded only in the subject's source documents. The following data will be documented for each AE:

- Description of the event
- Classification of “serious” or “nonserious”
- Date of first occurrence and date of resolution (if applicable)
- Severity
- Causal relationship to study drug(s)
- Action taken
- Outcome
- Concomitant medication or other treatment given

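### For an early stopper with no Safety Follow-up Visit, the SAP lets the treatment-emergent period end at the ETT Visit, short of the protocol's 28 days after last dose

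*SAP*

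**What the plan says.** SAP 9.1 (General Considerations) runs the TE period from first dose to "28 days after the last dose of the study drug or to the completion of study participation date, whichever occurs first". Completion is then defined by type of subject. The entry for early stoppers reads: "For subjects who prematurely discontinue study drug treatment but do not withdraw consent: the latest of ETT Visit, or Safety Follow-up Visit (if required").

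Protocol 12.3.1 ends the TE period at the Safety Follow-up Visit or, failing that, at "28 days after the last dose of the study drug for subjects who do not have a Safety Follow-up Visit". It gives the ETT Visit no role.

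Protocol 13.1.1.3 sets how long AEs are collected. "For enrolled subjects who do not have a Safety Follow-up Visit, the earliest of" two dates applies: 28 days after last dose, or "the ETT Visit, if that visit is 3 weeks or later following the last dose of study drug". The same section states: "All subjects will be queried, using nonleading questions, about the occurrence of AEs at each study visit".

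Protocol 9.1.4 asks for the ETT Visit as soon as possible after the decision to stop. It also says: "Subjects who prematurely discontinue treatment will also be required to complete the Safety Follow-up Visit", and "Subjects who prematurely discontinue treatment will continue to complete all the other scheduled study visits for assessments of efficacy".

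SAP Section 4 (Introduction) gives the SAP precedence where its methods differ from the protocol's.

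**The concern.** The SAP entry drops the condition that the protocol attaches to the ETT Visit. In the protocol, an ETT Visit can end AE collection only when it falls 3 weeks or more after last dose. In the SAP, an ETT Visit held two days after last dose can end the TE period, provided no Safety Follow-up Visit follows. The subject may still be attending study visits and being asked about AEs at each one.

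What falls after that date changes status. SAP 9.4.1 classifies AEs that begin or worsen beyond the TE period as post-treatment, while the overview and the SOC/PT tables (SAP 9.4.1.1 and 9.4.1.2) count treatment-emergent AEs (TEAEs). SAP 9.4.2 restricts the laboratory threshold tables to the TE period. Protocol 11.5.3 requires continued transaminase monitoring after discontinuation for elevated transaminases, so laboratory values after the ETT Visit are a realistic case.

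The effect runs one way. The shorter window can only remove events from the summary tables, and only in children who stopped drug.

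**Working it through.** The point rests on dates, not on a power or sample-size figure, so the plan has no figure of its own to reproduce. All days are counted from the last dose, for a subject who keeps consent and has no Safety Follow-up Visit. E is the day of the ETT Visit.

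**Rules**

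- SAP TE end (SAP 9.1) = min(28, E), because the ETT date is the only completion date available.
- Protocol TE end (Protocol 12.3.1) = 28.
- End of AE collection (Protocol 13.1.1.3) = 28 if E is below 21; otherwise min(28, E).
- Collected AE days outside the SAP's TE period = end of AE collection − SAP TE end.
- Shortfall against the protocol's TE period = 28 − SAP TE end.

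| E | SAP TE end | Protocol TE end | AE collection end | Collected AE days outside TE | Shortfall against protocol TE |
|---|---|---|---|---|---|
| 1 | 1 | 28 | 28 | 28 − 1 = 27 | 27 |
| 3 | 3 | 28 | 28 | 28 − 3 = 25 | 25 |
| 7 | 7 | 28 | 28 | 28 − 7 = 21 | 21 |
| 14 | 14 | 28 | 28 | 28 − 14 = 14 | 14 |
| 20 | 20 | 28 | 28 | 28 − 20 = 8 | 8 |
| 21 | 21 | 28 | 21 | 21 − 21 = 0 | 7 |
| 25 | 25 | 28 | 25 | 25 − 25 = 0 | 3 |
| 28 | 28 | 28 | 28 | 28 − 28 = 0 | 0 |

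From day 21 no collected AE is displaced, because AE collection itself stops at the ETT Visit. Only laboratory values drawn between a late ETT Visit and day 28 could still fall outside.

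**If the Safety Follow-up Visit is held.** Completion is then the later of the two visits. With an ETT Visit at day 3 and a Safety Follow-up Visit at day 21 or 28, the SAP and the protocol both end the TE period at 21 or 28. The ETT Visit cuts nothing.

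**Illustration in study days (assumed dates).** Last dose is on Day 20, the ETT Visit on Day 22, and the Safety Follow-up Visit is missed. The protocol's TE period ends on Day 20 + 28 = Day 48. An AE that begins on Day 26 and is reported at the Week 4 Visit (target Day 29) is a TEAE under the protocol. Under the SAP the TE period closed on Day 22 and the same AE is post-treatment.

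**Number of subjects.** The documents give no early-stopping rate. If the 10% dropout in the sample-size sections is assumed to be that rate, 0.10 × 65 = 6.5, so 6 or 7 children stop early. Only those without a Safety Follow-up Visit are affected, which gives 0 to about 7.

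**After the fix.** With E below 21 the TE period ends at day 28. With E at 21 or later it ends at min(28, E). Both match the end of AE collection, so the fifth column becomes 0 in every row.

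**The case against.** The strongest answer is that the affected group is nearly empty by design. The protocol requires the Safety Follow-up Visit of early stoppers, and if the ETT Visit would fall 3 weeks or later after last dose, the Safety Follow-up Visit takes its place (Protocol 9.1.4). Missed visits are the main route left. The SAP also does not say how its words about a required visit apply to one that was required and missed; taking the ETT date is a reading, though it is the only date the entry then supplies. This stands, and it limits the size of the problem. It does not supply the missing rule.

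Safety is also descriptive only (SAP 9.4), and the rule applies equally in all arms. No efficacy result depends on it.

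A reader might infer three stronger things that the documents do not support:

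- *That the data disappear from the report.* They do not. All AEs stay in the listings, SAEs and deaths are listed with a flag for TEAE status (SAP 9.4.1.1), the table of TEAEs and SAEs by preferred term may still count the SAEs (SAP 9.4.1.3), and the listing of elevated liver tests shows all time points (SAP 9.4.2).
- *That an AE or transaminase rise which led to stopping goes uncounted.* An event that began on treatment is already a TEAE by onset, and an elevation seen on treatment is already in the threshold table. At most, a later worsening or a higher threshold category is missed.
- *That a child who stops drug, attends Week 8 and enters the extension must lose most of the 28 days.* That child may fall under the SAP 9.1 entry for subjects who complete the study and roll over, since SAP 9.2.1 separates completing treatment from completing the study. Whether an early stopper may enter the extension depends on that study's criteria, which are not in these documents.

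**Conclusion.** The point holds, and it is minor. For an early stopper who keeps consent and has no Safety Follow-up Visit, the SAP's TE period can end at the ETT Visit, in conflict with Protocol 12.3.1 and without the 3-week condition of Protocol 13.1.1.3. No other SAP text restores the 28 days. When the ETT Visit is before day 21, AEs that begin or worsen in the rest of the collection period leave the TEAE tables: 8 days of collection at the latest such visit (day 20) and 27 at day 1. Unscheduled laboratory values drawn after the ETT Visit leave the threshold tables. The direction is toward fewer events in the summaries.

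This rests on two assumptions: that a missed Safety Follow-up Visit leaves the ETT date as the completion date, and, for the count of 0 to about 7 of 65, that the planned dropout rate equals early stopping. The documents do not show that any subject will be affected.

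**What to change.** Before database lock, reword the early-stopper entry in SAP 9.1 to agree with Protocol 12.3.1 and 13.1.1.3. Completion would be the date of the Safety Follow-up Visit if it was held. Otherwise it would be 28 days after last dose, or the ETT Visit if that visit took place at least 3 weeks after last dose. Also state which entry applies to an early stopper who attends Week 8 and then enrols in the extension, since two entries can be read to cover that child.

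The cost is one revised sentence and one clarification. The AE data are already collected under Protocol 13.1.1.3, and no visit, procedure or treatment rule changes. TEAE counts may rise slightly. Laboratory values drawn between an ETT Visit at day 21 or later and day 28 would remain outside the TE period, in line with the end of AE collection.
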